2 ABSTRACT

High grade gliomas, particularly glioblastoma, are the most common malignant primary brain tumors in adults(1). Surgical resection, when feasible, offers the best chance of alleviating the mass effect and increasing the likelihood of durable local control. Whether tumors are resected or deemed unresectable, the standard definitive treatment for high grade glioma is involved field radiation with concurrent and adjuvant temozolomide chemotherapy(2). Additional therapy with anti-VEGF therapies(3, 4) and wearable devices such as alternating electric fields(5) have improved progression free and overall survival modestly.

Unfortunately, most patients recur in the region of the primary tumor, ultimately leading to neurological progression and death in a majority of patients(6). One hypothesis for this progression in the region of the primary tumor has been the persistence of resistant clones, including glioma stem cells(7).

Neoadjuvant, preoperative chemo radiation has consistently shown improvements in local disease control or organ preservation in many cancers including head and neck(8), esophageal(9), rectal(10), bladder cancers(11) and sarcomas(12), leading to improvements in overall survival and limb or organ preservation.

Preoperative therapy has not been well studied in resectable glioblastoma. This study attempts to prospectively assess the feasibility and efficacy of preoperative chemoradiation in improving local control, as this is the predominant mode of failure in these patients leading to poor outcomes.

We plan to do this interventional study in two phases using the Simon two-stage Phase II study design(13). Please see section 5.9 on statistical analysis and plan. In the initial stage if there are no more than 3 unanticipated events after 9 patients, an additional 15 patients will be treated in the second stage of this Phase II study. If no more than 9 of the overall 24 patients overall progress in 8 months the study treatment would be considered significant and worthwhile studying in a future randomized phase III study, comparing preoperative study treatment with standard of care post postoperative chemoradiation to evaluate progression free and overall survival as the end point.

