5 STUDY DESIGN

5.1 Description

We plan to do this interventional study in two phases using the Simon two stage Phase II study design(13). Please see section 5.9 – Statistical methods. Given the novel approach of an existing treatment scheme, this two-stage design allows for safety and efficacy evaluation to proceed to the complete phase II study.

If the median progression free survival (PFS) in this study, meets significance at the completion of this study, it would form the basis to continue as a randomized phase III study with PFS as the primary study objective and overall survival as the secondary objective.

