5.7 Primary Endpoints

Phase II Simon Stage 1: No study related undue toxicity or progression in the first stage patients: Toxicity is defined as: progression precluding surgery, unanticipated neurological decompensation, non-completion of neoadjuvant therapy (other than protocol defined dose adjustments or discontinuation), treatment related delay of > 6 weeks to surgery, and/or major unforeseen surgical complication requiring repeat surgical intervention including other than non-life- threatening infection like meningitis/encephalitis or septicemia.

Phase II Stage 2 (Entire Cohort): Progression Free Survival: defined as MRI defined progression (increasing FLAIR, enhancement, diffusion and or perfusion) 3 months after completion of therapy (to allow for excluding pseudo progression) OR clinical progression with new or worsening neurological symptoms related to the tumor (by MRI or clinical correlation with location) and not due to non-tumor or study related symptoms.

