7.2 Protection of Human Subjects Against Risks

All the interventions in this study are standard of care. Hence there are no treatment related study related risks. However, there may be unforeseen the risks due to the sequence of treatment which is novel in this study. The purpose of this prospective study is to analyze if sequencing of standard of care makes is safe and could make a favorable difference as it has in other malignancies.

There are always potential risks related to loss of confidentiality (e.g., loss of insurance or employment, etc.) and all standard precautions will be taken to minimize the risks (eg. password protected files, encryption, locked cabinets)

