7.3 Data Monitoring Plan

The initial Feasibility Phase of the study may be limited to 10 patients. If 3 or more of these patients experience unexpected toxicities, the study will be discontinued. A data monitoring committee formulated specifically for the study would review the project from the Feasibility Phase to Phase II of the project.

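### The only numeric toxicity rules cover the first 9 or 10 patients; no prespecified rule uses toxicity in the remaining 14 to 15, and both final decision rules count progression only

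*Combined protocol and SAP*

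**What the plan says.** Safety is a stated purpose. Section 7.2 says: "The purpose of this prospective study is to analyze if sequencing of standard of care makes is safe". Section 5.1 says of the design that "this two-stage design allows for safety and efficacy evaluation to proceed to the complete phase II study".

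Three places describe the early safety decision, and they differ:

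- Abstract: "In the initial stage if there are no more than 3 unanticipated events after 9 patients, an additional 15 patients will be treated".
- Section 7.3: "The initial Feasibility Phase of the study may be limited to 10 patients", followed by "If 3 or more of these patients experience unexpected toxicities, the study will be discontinued".
- Section 5.7 gives no number: "Phase II Simon Stage 1: No study related undue toxicity or progression in the first stage patients". Its definition begins "Toxicity is defined as: progression precluding surgery, unanticipated neurological decompensation, non-completion of neoadjuvant therapy" and goes on to treatment-related delay to surgery and major surgical complications needing re-operation.

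The final decision rests on progression. The Abstract says: "If no more than 9 of the overall 24 patients overall progress in 8 months the study treatment would be considered significant". Section 5.9.2 needs 17 or more of 25 patients free of progression at 7 months. Neither mentions toxicity.

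Other oversight exists. Under section 6.1, adverse events are monitored throughout and the investigator reports every 3 months to an independent board, in a sentence tied to the feasibility part. Under section 7.3 a committee reviews the move to phase II. Under section 6.3 serious adverse events go to the IRB. None of these has a stated criterion.

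**The concern.** The order of treatment is the experimental element, and its safety is one of the questions asked. The early look is small, and the plan states neither the event rate it is meant to detect nor its chance of detecting it. More than half of the patients are treated afterwards, yet no prespecified rule uses their toxicity.

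For example, 1 event in the first 10 patients and 8 in the next 15 gives 9/25 = 36%. That triggers no toxicity rule. The treatment could still meet the final rule in section 5.9.2, provided that at least one of the nine events is not also a progression. At stake is a phase III recommendation made without any planned use of most of the safety data.

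**Working it through.** **The plan's own figures.** The only operating characteristics stated are for efficacy: type I error 0.05 and power 80% (section 5.9.2). With n1 = 11, r1 = 6, n = 25 and rejection at 17 or more,

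P(reject | p) = Σ over x = 7 to 11 of b(x; 11, p) × P(Bin(14, p) ≥ 17 − x).

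This gives 0.0458 at p = 0.50 and 0.8005 at p = 0.75, so the efficacy design reproduces. Nothing comparable is stated for toxicity.

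**Inputs for toxicity.** Section 7.3 passes with 2 or fewer of 10. The Abstract passes with 3 or fewer of 9; it says events, which I count as patients. True event rates are assumptions.

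**Chance of passing the early look.** P(X ≤ 2 | n = 10, p) and P(X ≤ 3 | n = 9, p). At p = 0.30:

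- 7.3: 0.0282 + 0.1211 + 0.2335 = 0.383.
- Abstract: 0.0404 + 0.1556 + 0.2668 + 0.2668 = 0.730.

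| True event rate | 7.3 (≤2 of 10) | Abstract (≤3 of 9) |
|---|---|---|
| 10% | 93% | 99% |
| 20% | 68% | 91% |
| 25% | 53% | 83% |
| 30% | 38% | 73% |
| 40% | 17% | 48% |

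**What a pass excludes.** The exact (Clopper-Pearson) one-sided 95% upper bound is the 0.95 quantile of Beta(x + 1, n − x). It is 50.7% for 2/10 and 65.5% for 3/9. Even 0/10 leaves 25.9%.

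**The example.** 9/25 has an upper bound of 54%. If all nine events were progressions, 25 − 9 = 16 patients would be progression-free, one short of 17. At least one event must therefore be something other than progression.

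**Illustrative cumulative limits.** Stop or review at ≥3/10, ≥5/15, ≥6/20 or ≥7/25. The figures come from an exact recursion: at each look, convolve the surviving counts with the next binomial block and remove those at or over the limit.

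| True event rate | Single look at 10 | By patient 20 | All four looks |
|---|---|---|---|
| 10% | 7.0% | 7.4% | 7.6% |
| 15% | 18% | 20% | 21% |
| 20% | 32% | 37% | 41% |
| 30% | 62% | 72% | 78% |
| 40% | 83% | 93% | 96% |

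**Cost of making the upper bound a go condition.** With an assumed 30% ceiling, 3/25 passes (bound 28.2%) and 4/25 does not (33.0%). Combined with the looks above, a treatment with a true 10% rate would fail 25% of the time, and one with a true 15% rate 54%.

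**The case against.** A reader might infer that later harm cannot alter the outcome. The documents do not support that. Adverse event monitoring, board reports, the committee and IRB reporting could all lead to action by judgement. Tumour-related neurological worsening counts as progression under section 5.7, and progression that precludes surgery plausibly does too, so part of the toxicity can lower the efficacy result. What stands is narrower: none of these bodies has a criterion, the board's reporting is tied to the feasibility part, and section 5.7 keeps study-related symptoms out of clinical progression.

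A reader might also infer that a treatment seriously harming 30% of patients passes up to 73% of the time. The composite also counts non-completion of neoadjuvant therapy and delay to surgery, which are feasibility failures and not necessarily harm, so 30% is a composite rate. It is also assumed. The 73% belongs to the Abstract's rule alone and would fall if several events in one patient each counted. Read literally as zero events, section 5.7 would let a 30% rate through only 2% to 4% of the time (0.7^11 to 0.7^9). That is a further reason to reconcile the texts.

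Nor does the protocol say that passing the look demonstrates safety; it uses the look to decide whether to proceed.

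Finally, it can be argued that cumulative boundaries are a matter of taste in a 25-patient single-arm study of standard components, and that a look at patient 25 can no longer prevent enrolment. The second point is right: by patient 20, detection at 30% is 72%, not 78%. On the first, this is a design choice, but safety of the sequence is a stated purpose and the change is cheap.

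**Conclusion.** The point holds in a limited form. Numeric toxicity rules stop at patient 9 or 10. Nothing prespecified uses toxicity in the remaining 14 to 15 patients, and the final decision rules do not refer to it. Across assumed true composite rates of 20% to 40%, the early look is passed 68% to 17% of the time under 7.3 and 91% to 48% under the Abstract. A pass is a reason to continue accrual; it does not exclude a high event rate.

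These figures assume independent patients, one count per patient, and that every composite event is classed as unexpected or unanticipated. If some are not, passing becomes more likely. The gap remains whichever early count is kept, although its size differs. This is an improvement the sponsor should make, not an error that invalidates the efficacy design.

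**What to change.** 1. Reconcile section 7.3, the Abstract and section 5.7 on cohort size, limit, and whether patients or events are counted. Which early rule to keep is for the sponsor.
2. In section 7.3, carry the same event definition forward as a cumulative trial-level review limit over all 25 patients, reviewed by the existing board. The sponsor should state the unacceptable rate, the limits and the resulting stop probabilities. The 5/15, 6/20 and 7/25 limits are an illustration only.
3. Report the cumulative event rate in all 25 patients with its exact one-sided 95% upper bound. It would help to show serious harm and feasibility failures separately.
4. In the Abstract and section 5.9.2, state that a phase III recommendation also requires that the cumulative limit was not crossed. Do not make the upper bound itself a go condition without stating its cost, as shown above.

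The cost is amendment wording and a short boundary table, with no extra patients, visits or staff. The downside is more stops at lower event rates. With the illustrative limits these rise from 7.0% to 7.6% at a 10% rate, from 18% to 21% at 15%, and from 32% to 41% at 20%.
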